4.2.2 Secondary efficacy analysis

The secondary efficacy variables are

- Number of recovered subjects per treatment group in total and until each individual treatment day. Mean and median time until recovery per treatment group.
- Time until recovery, defined by date and time of the evacuation of the first of two consecutive normal stools.

Time until recovery, number of recovered subjects per treatment group in total and until each individual treatment day and mean and median time until recovery per treatment group will be estimated Kaplan Meier analysis as described for the primary endpoint.

- Global Physician Assessment at the end of treatment:
 - \circ 1 = Complete relief of acute diarrhea,
 - \circ 2 = marked improvement of acute diarrhea,
 - \circ 3 = moderate improvement of acute diarrhea,
 - 4 =slight improvement of acute diarrhea,
 - \circ 5 = no change in acute diarrhea,
 - \circ 6 = worsening of acute diarrhea.

Frequencies table will be performed for the Global Physician Assessment at the end of treatment by GPA score and by success rating. Treatment will be rated as success when the GPA score equals 1 or 2.

Description of the subgroup analysis is presented in the Section 4.2.3 of the SAP.

The comparisons of treatment arms using Fisher exact test will be performed by proportion of patients with Global Physician Assessment success at the end of treatment.

SAS code for the analysis:

PROC FREQ DATA = [dataset name]; WEIGHT [GPA frequency] / ZEROS; TABLES [GPA yes/no level] * [Arm] / EXACT FISHER;

RUN;

If SAS code produces the "Row or column sum zero. No statistics computed for this table." output due to insufficient memory available to complete the Fisher exact computations, then the p-value should be assumed as equal 1.0000.

• For toilet trained children and adolescents: number of stools per day as well as number of watery stools per day from start of treatment and until end of study treatment.

Number of stools and number of watery stools will be presented descriptively per treatment group and cumulatively until each day of treatment.

4.2.3 Other efficacy analysis

Additionally, duration of diarrhea and time to recovery will be analyzed using Cox regression model where treatment group, age group, and dosing/weight group will be included as covariates. Relative risk will be presented for each covariate with 95% confidence intervals (Relative risk is referred to as "Hazard ratio" in the output from PROC PHREG SAS procedure).

SAS code for the analysis:

PROC PHREG DATA = [dataset name]; CLASS [arm variable] (ref=[reference level]) [age group] (ref=[reference level]) [weight/dosing category] (ref=[reference level]); MODEL [time variable] * [censor variable] =

[arm variable] [age group] [weight/dosing category] / RL;

RUN;

The results of the exploratory analyses using Cox regression model will be provided in appropriate tables with the main results (see 10.1.4.1.2.1; 10.1.4.1.2.2; 10.1.4.1.5.1; 10.1.4.1.5.2; 10.1.4.2.2.1 and 10.1.4.2.2.2 table shells).

The comparisons by subgroup for GPA score success rating using Fisher exact test will be performed using the following SAS code:

PROC FREQ DATA = [dataset name];

WEIGHT [GPA frequency] / ZEROS;

TABLES [GPA yes/no level] * [Arm] / EXACT FISHER;

BY [age subgroup variable];

RUN;

If SAS code produces the "Row or column sum zero. No statistics computed for this table." output due to insufficient memory available to complete the Fisher exact computations, then the p-value should be assumed as equal 1.0000.

The results of the exploratory analyses will be provided in appropriate tables with the main results (see Table 10.1.4.2.3), no adjustment for multiplicity will be done due to the exploratory nature of analyses.

4.3 Safety analysis

The Safety Sample will be used for the analysis of the safety and tolerability data.

Descriptive statistics for all safety and tolerability data will be presented by treatment arm and by stratification level (Age Category).

AEs are considered treatment emergent (TE) if they start or worsen at or after the first administration of study drug and before or on the day of last administration of study drug plus a gap period of 1 day (24 hours).

AEs will be reported on a per-subject basis, i.e. counting subjects rather than events. This means that if a subject suffers the same AEs repeatedly during the applicable study period, the event will be counted only once for that period. Repeated events per subject will be summarized according to the following rule: if a subject suffered the same AE more than once, the event will be assigned the worst severity, the closest relationship to the study drug and the earliest starting date. Only treatment emergent AEs will be reported. In the listings, however, all occurrences of the AEs will be presented.

For each unique treatment, treatment emergent AEs will be summarized per primary SOC, per HLT by primary SOC and per PT by HLT and primary SOC. Severity and drug-event relationship of treatment emergent AEs are summarized separately. Non-TEAEs will be listed.

Vitals signs: Height (m), Weight (kg), Systolic Blood Pressure (mmHg), Diastolic Blood Pressure (mmHg), Pulse (bpm), including changes from baseline will be summarized. A frequency table will be presented for markedly abnormal values (presented in the table categories includes "to high", "to low" and "normal" levels based on normal ranges).

Temperature data will be presented in appropriate listing only.

RACE3003 clinical study was conducted with the involvement of local laboratories, thus local normal ranges have been used in each particular site (the ranges are presented below). Additional footnote ("Created *
* based on site specific ranges.") will be presented for appropriate tables and listings in the statistical analysis report.

Normal Heart Rate by Age (beats/minute)											
Site Age	1	2	3	4	5	6	7	8	9		
1-12 month	100-140	100-190	100-190	100-160	100-190	100-190	110-170	100-190	100-190		
1-3 years	98-120	98-140	95-110	98-140	98-140	98-140	100-130	98-140	98-140		
3-6 years	80-105	80-120	80-120	80-120	80-120	80-120	85-115	80-120	80-120		
6-9 years	75-90	75-118	75-110	75-118	75-118	75-118	75-105	75-118	75-118		
9-12 years	70-90	60-100	60-100	60-100	60-100	60-100	70-90	60-100	60-100		
12-18 years	70-90	60-100	60-100	60-100	60-100	60-100	70-90	60-100	60-100		

Normal Systolic Blood Pressure by Age (mm Hg)											
Site Age	1	2	3	4	5	6	7	8	9		
1-12 month	80-112	90-112	85-105	90-112	90-112	90-112	75-80	90-112	90-112		
1-3 years	90-112	100-112	85-110	100-112	100-112	100-112	80-85	100-112	100-112		
3-6 years	100-116	100-116	85-115	100-116	100-116	100-116	90-95	100-116	100-116		
6-9 years	100-122	100-122	95-120	100-122	100-122	100-122	95-105	100-122	100-122		
9-12 years	100-126	110-126	110-125	110-126	110-126	110-126	105-115	110-126	110-126		

Normal Systolic Blood Pressure by Age (mm Hg)											
Site Age	Site 1 2 3 4 5 6 7 8 9										
12-18 years	110-120	110-136	110-130	110-136	110-136	110-136	110-120	110-136	110-136		

Normal Diastolic Blood Pressure by Age (mm Hg)											
Site Age	1	2	3	4	5	6	7	8	9		
1-12 month	50-74	50-74	45-60	50-74	50-74	50-74	50-74	50-74	50-74		
1-3 years	60-74	60-74	50-60	60-74	60-74	60-74	50-55	60-74	60-74		
3-6 years	60-76	60-76	55-60	60-76	60-76	60-76	50-60	60-76	60-76		
6-9 years	60-78	60-78	55-70	60-78	60-78	60-78	65-70	60-78	60-78		
9-12 years	70-82	60-82	55-70	70-82	70-82	70-82	70-75	70-82	70-82		
12-18 years	70-86	60-86	55-70	70-86	70-86	70-86	70-80	70-86	70-86		

Temperature (C)										
Site Age	1	2	3	4	5	6	7	8	9	
Axillary	36,1-	35,9-	36,3-	36,3-	36,3-	36,3-	36,3-	36,3-	36,3-	
	36,9	36,9	36,9	36,9	37,0	36,9	36,9	36,9	36,9	
Oral	36,8-	36,2-	36,8-	36,8-	36,8-	36,8-	36,8-	36,8-	36,8-	
	37,3	37,3	37,3	37,3	37,3	37,3	37,3	37,3	37,3	
Rectal	37,1-	36,9-	37,3-	37,3-	37,3-	37,3-	37,3-	37,3-	37,3-	
	37,9	37,9	37,7	37,7	38,0	37,7	37,7	37,7	37,7	
Tympanic	36,1-	36,5-	37,3-	37,3-	37,3-	37,3-	37,3-	37,3-	37,3-	
membrane	36,9	37,5	37,7	37,7	37,7	37,7	37,7	37,7	37,7	
Skin / Temporary artery	36,1- 36,9	36,3- 36,9								

Physical Examination will be summarized by subgroup (toilet trained, not toilet trained and overall).

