**Screening and Enrolment (Day 1, Visit 1)**

Subjects presenting with acute diarrhea will be evaluated for eligibility. They will undergo a physical examination including vital signs, a review of their medical history and concomitant medication. If the subjects are eligible, demographics, number of stools during the last 24 hours will be assessed as baseline values. The subjects will be randomized to Racecadotril plus ORS or ORS alone. On Day 1 the subject will start with study treatment. The starting dose will either be the noon or the evening dose.

Treatment period (until recovery, maximally five days)

Subjects will be treated with Racecadotril three times daily according to the body weight dose requirement on an out-patient or in-patient basis for maximum 5 days in addition to ORS or with

Name of Sponsor: Abbott Laboratories GmbH	Name of Finished Product: Hidrasec Infants: Granules for Oral Suspension 10 mg Hidrasec Children: Granules for Oral Suspension 30 mg Hidrasec: 100 mg capsules	Name of Active Ingredient(s): Racecadotril
-----------------------------------------------------	--------------------------------------------------------------------------------------------------------------------------------------------------------------------------------	------------------------------------------------------

ORS alone. ORS will be prescribed by the investigator. The parent/caregivers will be instructed to stop treatment when the patient recovered. Recovery is defined by the evacuation of the first of two consecutive normal stools. In the evening of each day, the parent(s)/caregiver(s) will fill in the diaries, documenting date and time of each individual stool, the stool consistency of each stool, ORS amount and the study drug intake. AEs are to be reported on an ongoing basis. Treatment will stop at recovery or after the morning dose of day 6, if not recovered.

End of treatment (at recovery or Day 6, Visit 2)

The last dose of study drug intake will be the morning dose of day 6, if not recovered earlier. The parent(s)/caregiver(s) will visit the site for the end of study visit of the child. Data on vital signs, AEs, physical examination and concomitant medication will be collected. The parent(s)/caregiver(s) will return the diaries and unused medication.

Safety follow-up

A phone call will be performed at 5-7 days after end of the treatment period or recovery for the safety follow-up.

Table 1. Flow Chart of Study Assessments

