3.3 Safety Objective(s)

To evaluate the safety and tolerability of Racecadotril together with oral rehydration solution (ORS) versus ORS alone in infants, children and adolescents with acute diarrhea by adverse events, physical examination and vital signs.

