10.1 General Definitions and ConventionsTime-Related Definitions

All assessment dates will be related to the first day of study drug administration. This first day of drug administration is referred to as Day 1. Day -1 is the day that is preceding Day 1 and a Day 0 will not be defined.

The baseline period will be defined as the period from informed consent to the first study drug administration. The baseline value for a variable is defined as the last non-missing value collected before first study drug administration.

The endpoint value for efficacy variables is defined as the last non-missing value assigned to treatment for the subject.

All variables planned to be measured at one or more time points and supposed to be time-related will be windowed.

Coding Systems

AEs and medical history Investigator terms will be assigned to a lowest level term (LLT) and a preferred term (PT) and will be classified by high level term (HLT), high level group term (HLGT) and primary system organ class (SOC) according to the MedDRA thesaurus.

Concomitant medications will be classified according to active drug substance using the WHO drug dictionary. The generic name, the preferred name and the WHO name will be assigned.

In addition, the Anatomical Therapeutic Chemical (ATC) classes will be assigned to the drug ID. ATC codes are defined to the 4th level. For each medication, the primary ATC class will be assigned manually based on the generic name and the reason for use.

Default Summary Statistics

The default summary statistics for quantitative and ordinal variables will be the number of observations (n), mean, standard deviation (SD), median, minimum (Min) and maximum (Max) for subjects with data. Any other summary statistics will be described on an individual basis.

Default Frequency Tabulations

For qualitative variables, per category the numbers and frequencies of subjects with non-missing data (n, %) will be the default summary presentation, and if appropriate and present, the number of missing values.

For AEs, medical history and concomitant medications, however, the denominator for the percentage calculation will be the number of subjects at risk for the particular treatment arm. A subject will be considered at risk if the subject is in the safety sample and entered the respective study period.

Subject Listings

Individual subject listings will be produced for all raw data and a selection of the derived data.

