10.4 Safety

The safety sample will be used for the analysis of the safety and tolerability data.

AEs are considered treatment emergent (TE) if they start or worsen at or after the first administration of study drug and before or on the day of last administration of study drug plus a gap period of 1 day.

AEs will be reported on a per-subject basis, i.e. counting subjects rather than events. This means that if a subject suffers the same AEs repeatedly during the applicable study period, the event will be counted only once for that period. Repeated events per subject will be summarized according to the following rule: if a subject suffered the same AE more than once, the event will be assigned the worst severity, the closest relationship to the study drug and the earliest starting date. Only treatment emergent AEs will be reported. In the listings, however, all occurrences of the AEs will be presented.

For each unique treatment, treatment emergent AEs will be summarized per primary SOC, per HLT by primary SOC and per PT by HLT and primary SOC. Severity and drug-event relationship of treatment emergent AEs are summarized separately. Non-TEAEs will be listed.

Vitals signs, including changes from baseline will be summarized. A frequency table will be presented for markedly abnormal values.

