9.2 Tables, Listings and Figures

9.2.1 Tables

For the shells of the non-standard tables, see Section 10.1.

				Produced	for:	
Output Code	Clinical Domain	Output Number	Title	Headline Results	SMT	Interim Analysis
DST001	Subject Disposition	10.1.1.1	Subject Disposition - All Subjects Allocated to Treatment Subject Sample			
DVT001	Protocol Deviations	10.1.1.2	Protocol Deviations – All Subjects Allocated to Treatment Subject Sample			
DVT002	Protocol Deviations	10.1.1.3	Subject Samples - All Subjects Allocated to Treatment Subject Sample			
DMT002	Demographic Data	10.1.1.5	Demographics – Safety Sample			
DMT002	Demographic Data	10.1.1.6	Demographics –Full Analysis Subject Sample			
VST003	Vital Signs	10.1.1.8	Other Baseline Characteristics – Safety Sample			
VST003	Vital Signs	10.1.1.9	Other Baseline Characteristics – Full Analysis Subject Sample			
MHT001	Medical History	10.1.1.10	Medical History – All Subjects Allocated to Treatment Subject Sample			
MHT001	Medical History	10.1.1.11	Medical History – Safety Sample			
MHT001	Medical History	10.1.1.12	Medical History – Full Analysis Subject Sample			
NST001	Medical History	10.1.1.13	Main Diagnosis - All Subjects Allocated to Treatment Subject Sample			
NST002	Medical History	10.1.1.14	Main Diagnosis - Safety Sample			
NST003	Medical History	10.1.1.15	Main Diagnosis - Full Analysis Subject Sample			
CMT001	Concomitant Medications	10.1.1.16	Concomitant Medications – All Subjects Allocated to Treatment Subject Sample			
CMT001	Concomitant Medications	10.1.1.17	Concomitant Medications – Safety Sample			

30

				Produced	for:	
Output Code	Clinical Domain	Output Number	Title	Headline Results	SMT	Interim Analysis
CMT001	Concomitant Medications	10.1.1.18	Concomitant Medications – Full Analysis Subject Sample			
DAT001	Treatment Compliance	10.1.1.19	Compliance to Study Drug – All Subjects Allocated to Treatment Subject Sample			
DAT001	Treatment Compliance	10.1.1.20	Compliance to Study Drug – Safety Sample			
DAT001	Treatment Compliance	10.1.1.21	Compliance to Study Drug – Full Analysis Subject Sample			
AET001	Adverse Events	10.1.3.1.1	Overall Summary of Adverse Events – Safety Sample			
AET002	Adverse Events	10.1.3.1.2	Incidence of TEAEs – Safety Sample			
AET005	Adverse Events	10.1.3.1.3	Incidence of TEAEs With a Reasonable Possibility for a Causal Relationship (Investigator's Judgment) – Safety Sample			

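### Adverse-event tables count only to last dose plus 1 day, and treatment stops at recovery, so the counting window is shorter in the arm that recovers faster

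*SAP*

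**What the plan says.** Under SAP 4.3 an event is treatment-emergent if it begins or worsens from the first dose of study drug and "before or on the day of last administration of study drug plus a gap period of 1 day (24 hours". Protocol 10.4 has the same rule without the hours: "before or on the day of last administration of study drug plus a gap period of 1 day". SAP 4.3 adds "Only treatment emergent AEs will be reported", with the remaining events going to listings. The unit is the subject: "AEs will be reported on a per-subject basis, i.e. counting subjects rather than events". For the percentages, protocol 10.1 states that "the denominator for the percentage calculation will be the number of subjects at risk for the particular treatment arm". Results are shown by arm.

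Five of the six adverse-event tables in SAP 9.2.1 are limited by title to treatment-emergent events. The sixth, "Overall Summary of Adverse Events", is not, but its shell is not in the documents and the SAP 4.3 text restricts reporting in any case. SAP 5.5.2 tabulates treatment duration separately.

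On stopping, the protocol synopsis (Treatment period) says "Treatment will stop at recovery or after the morning dose of day 6, if not recovered", and protocol 8.1 repeats it. Event collection runs longer: to a phone call 5-7 days after recovery or end of treatment, then passively to 30 days (protocol synopsis and 9.1.1).

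**The concern.** The safety objective in protocol 3.3 is comparative: "To evaluate the safety and tolerability of Racecadotril together with oral rehydration solution (ORS) versus ORS alone". A subject who recovers early stops treatment early, and that subject's counting window closes about a day later. Faster recovery is the effect under test. If racecadotril works as planned, its subjects are therefore observed, for tabulation purposes, for less time than control subjects. A percentage with subjects as denominator turns less time into fewer events. A reader of the incidence tables could take part of that gap for better tolerability.

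A second, smaller point is that the window rule refers to *study drug* without naming the product that applies in the ORS arm. Protocol 7.8 uses the term for racecadotril, whereas SAP 6.1.2 bounds the control treatment period by ORS doses.

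**Working it through.** **Inputs.** Mean duration of diarrhea is 64 h (placebo) and 40 h (racecadotril), with recovery percentages at 24, 50, 72, 96 and 120 h and 62 subjects per arm (all protocol 10.8). The gap after last dose is 1 day (SAP 4.3). The adverse-event rate is not given, so 10% and 20% on ORS are assumed.

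**1. Check of the planning means.** The area under the unrecovered curve to 120 h (trapezoid rule, from the protocol's recovery table) is:

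- Control: 21.80 + 18.97 + 11.53 + 7.72 + 5.17 = 65.2 h
- Racecadotril: 18.41 + 10.83 + 5.03 + 3.08 + 1.82 = 39.2 h

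Both are within about 2% of the stated 64 and 40 h.

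**2. Ratio of mean windows.** The ratio is (40 + s + g)/(64 + s + g). Here s is the time dosing runs past the last watery stool, taken as equal in both arms because recovery is recognised only later. The tail g is 24 h, or up to 48 h because the rule runs to the *day* of last dose plus 1 day.

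| s | g = 24 h | g = 48 h |
|---|---|---|
| 0 h | 64/88 = 0.73 | 88/112 = 0.79 |
| 12 h | 76/100 = 0.76 | 100/124 = 0.81 |
| 24 h | 88/112 = 0.79 | 112/136 = 0.82 |

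Piecewise-exponential curves through the recovery percentages, with dosing capped at 108-120 h and s = 0, give 0.70-0.71 (24 h tail) and 0.76-0.77 (48 h tail). The overall range is 0.70 to 0.82.

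**3. Effect on incidence at an equal, constant hazard.** If the ORS incidence is p and the window ratio is r, the racecadotril incidence is 1 − (1 − p)^r.

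- r = 0.727, p = 10%: 1 − 0.90^0.727 = 7.38%, a shortfall of 62 × 0.0262 = 1.6 subjects
- r = 0.727, p = 20%: 1 − 0.80^0.727 = 14.98%, a shortfall of 62 × 0.0502 = 3.1 subjects
- r = 0.824, p = 10%: 8.31%, a shortfall of 1.05, or about 1.1 subjects
- r = 0.824, p = 20%: 16.8%, a shortfall of 2.0 subjects

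Averaging over the recovery curves instead of using the means (maximum dosing 114 h) gives 1.8 and 3.4 subjects for s = 0 with a 24 h tail. For s = 12-24 h with a 48 h tail it gives 1.1 to 2.4. The range is about 1.1 to 3.4 subjects of 62.

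**4. If the hazard falls after recovery.** Let the hazard after the end of diarrhea be a fraction f of the hazard during it. Part of any shortfall is then real, because a shorter illness brings fewer events. The artefact is the shortfall in the planned table minus the shortfall in a 120 h common-window table, here in subjects of 62 at p = 10% / 20% with s = 0:

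| f | 24 h tail | 48 h tail |
|---|---|---|
| 1 | 1.8 / 3.4 | 1.4 / 2.6 |
| 0.5 | 1.1 / 2.1 | 0.9 / 1.7 |
| 0.25 | 0.6 / 1.2 | 0.5 / 1.0 |
| 0 | 0 / 0 | 0 / 0 |

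**5. Against sampling error.** The standard error of the difference in counts is √(62 × [0.10 × 0.90 + 0.0738 × 0.9262]) = 3.1 at 10%, and √(62 × [0.20 × 0.80 + 0.1498 × 0.8502]) = 4.2 at 20%. The artefact stays below one standard error in each case.

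**6. No efficacy difference.** With equal durations and the same stopping rule in both arms, r = 1 and the artefact is nil.

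**The case against.** The case for leaving the plan alone has weight. Safety is descriptive, with no between-arm test of adverse events. No event rate is given, so every count above is conditional, and the artefact is smaller than the sampling error. Nothing is lost from the record: later events are collected and listed, and tabulated treatment duration shows a reader that exposure differs. The standard table shells sit in a separate sponsor module that is not in the documents, so further displays there cannot be ruled out. A common-window table is also imperfect. Diary recording may stop at recovery (protocol 8.3), so later events rest mainly on one phone call, and ascertainment is thinner in faster recoverers.

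All of this limits the size of the point and its urgency. It does not remove the point: imprecision does not excuse a known directional distortion, and a duration table leaves the incidence tables unadjusted.

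Two stronger readings are tempting. First, a reader might infer from protocol 7.8 that ORS subjects have received no study drug and so fall outside the safety sample. The documents do not support this. That sample requires a dose of *study medication* (protocol 10.2, SAP 4.1), a different term that 7.8 does not define. SAP 4.3 presents safety by arm, and SAP 6.1.2 gives the control arm a usable period from first to last ORS dose. Second, because SAP 5.5.1 allows ORS to be coded as needed, and protocol 4.1 words the stop instruction in terms of study drug, a reader might infer that ORS ends at a different time from racecadotril and that the bias could grow or reverse. The synopsis and protocol 8.1 stop treatment at recovery without limiting this to racecadotril, and no passage states a shift in one arm only. As-needed use makes such a shift possible, but it cannot carry the magnitude.

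**Conclusion.** The point holds at moderate strength. The adverse-event tables named in the plan use a window whose length depends on the efficacy outcome. If racecadotril shortens diarrhea as planned, its window is on average about 0.70 to 0.82 of the control window. At an assumed 10-20% incidence on ORS and a constant, equal hazard, that is worth about 1.1 to 3.4 fewer tabulated subjects of 62 on racecadotril with no true difference.

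The estimate rests on the planning durations, an assumed event rate, a tail of 24-48 h, and dosing that ends 0-24 h after the last watery stool by the same rule in both arms. The artefact shrinks if the hazard drops after recovery, and is nil if the hazard drops to zero or efficacy is equal. Being within about one standard error, it would not by itself decide a safety conclusion, and the observed counts in one trial could go either way. It is a correctable weakness in a comparative display, not a loss of safety data. The wording of the ORS-arm window is a secondary matter of clarity, since SAP 6.1.2 already gives a workable bound.

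**What to change.** In SAP 4.3 and the SAP 9.2.1 table list, keep the last dose plus 1 day tables as the on-treatment display. Add one by-arm incidence table of all adverse events over a common window from first dose. About 120 h is feasible in followed subjects, because the phone call comes at least 5 days (5 × 24 = 120 h) after recovery or end of treatment. Footnote that ascertainment after recovery is less intensive and rests mainly on that call.

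As a supporting clarification, state in SAP 4.3 which product's first and last dose bounds the window in each arm, and reconcile the use of *study drug* in protocol 7.8 with the ORS element in SAP 6.1.2.

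The cost is one table, one footnote and one definition, all from data already collected. The downsides are the thinner late ascertainment and the counting of some post-treatment events unrelated to treatment. On-treatment events after 120 h would appear only in the on-treatment tables, which is a reason to keep both displays.

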AET006	Adverse Events	10.1.3.1.4	Incidence of TEAEs by Maximum Severity (Investigator's Judgment) – Safety Sample			
AET007	Adverse Events	10.1.3.1.5	Incidence of TESAEs – Safety Sample			
AET008	Adverse Events	10.1.3.1.6	Incidence of TEAEs Leading to Study Termination – Safety Sample			
VST001	Vital Signs	10.1.3.2.1	Summary of Vital Signs – Safety Sample			
VST002	Vital Signs	10.1.3.2.2	Incidence of Markedly Abnormal Vital Signs – Safety Sample			
NST004	Physical Examination	10.1.3.3.1	Physical Examination by subgroup (Toilet trained / Not toilet trained) – Safety Sample			
NST005	Exposure	10.1.3.4.1	Treatment duration – Safety Sample			
NST006	Exposure	10.1.3.4.2	Cumulative dose by weight (mg/kg) – Safety Sample			

				Produced	for:	
Output Code	Clinical Domain	Output Number	Title	Headline Results	SMT	Interim Analysis
NST007	Subject Status	10.1.4.1.1	Duration of diarrhea: time to last diarrheal/watery stool before recovery by days. Kaplan-Meier analysis – Full Analysis Subject Sample			
NST008	Subject Status	10.1.4.1.2.1	Duration of diarrhea. Descriptive statistics (in hours) and comparison results – Full Analysis Subject Sample			
NST009	Subject Status	10.1.4.1.2.2	Duration of diarrhea. Cox Regression Model – Full Analysis Subject Sample			
NST010	Subject Status	10.1.4.1.3.1	Duration of diarrhea. Descriptive statistics (in hours) and comparison results for age group from 3 to < 24 month – Full Analysis Subject Sample			
NST011	Subject Status	10.1.4.1.3.2	Duration of diarrhea. Descriptive statistics (in hours) and comparison results for age group from >= 2 to <12 years – Full Analysis Subject Sample			
NST012	Subject Status	10.1.4.1.3.3	Duration of diarrhea. Descriptive statistics (in hours) and comparison results for age group from 12 to < 18 years – Full Analysis Subject Sample			
NST013	Subject Status	10.1.4.1.3.4	Duration of diarrhea. Descriptive statistics (in hours) and comparison results for weight/dosing category infants less than 9 kg – Full Analysis Subject Sample			
NST014	Subject Status	10.1.4.1.3.5	Duration of diarrhea. Descriptive statistics (in hours) and comparison results for weight/dosing category infants from 9 kg to < 13 kg – Full Analysis Subject Sample			

				Produced	for:	
Output Code	Clinical Domain	Output Number	Title	Headline Results	SMT	Interim Analysis

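### The table of markedly abnormal vital signs is cut at ordinary site normal limits, so its label claims more than its rule measures

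*SAP*

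**What the plan says.** Protocol 10.4 commits to the output without giving limits: "A frequency table will be presented for markedly abnormal values". SAP 4.3 repeats the commitment and supplies the only classification rule in either document: "A frequency table will be presented for markedly abnormal values (presented in the table categories includes 'to high', 'to low' and 'normal' levels based on"; the sentence ends by naming normal ranges as the basis. It then states that "local normal ranges have been used in each particular site (the ranges are presented below", and prints limits by age band for nine sites.

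The output list in SAP 9.2.1 gives table 10.1.3.2.2 (code VST002) the title "Incidence of Markedly Abnormal Vital Signs – Safety Sample". SAP 9.2.2 gives listing 12.2.8.8 (code VSL004) a title that also refers to markedly abnormal vital signs. SAP 4.3 further asks for a footnote, on the affected tables and listings, saying that site-specific ranges were used.

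**The concern.** A normal limit and a limit for marked abnormality are different things. A three-class scheme cut at normal limits has no class for a marked departure: a reading 1 mmHg beyond the limit is counted with one far beyond it. The title of table 10.1.3.2.2 nevertheless says that the readings counted are markedly abnormal.

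Vital signs are one of the three safety measures named in the safety objective, beside adverse events and physical examination. A reader of the report could take the table at its word and conclude that marked blood pressure or pulse abnormalities were common in both arms. A reader looking for a real difference in marked abnormality would find it mixed, within this table, with small excursions.

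**Working it through.** **1. Rule against label (no assumption needed).** Take systolic pressure at 1–3 years, sites 1 to 9 in order: "1-3 years 90-112 100-112 85-110 100-112 100-112 100-112 80-85 100-112 100-112". At site 2 the range is 100–112, so 113 is classed too high, in the same class as any larger value. Nothing in SAP 4.3 or protocol 10.4 adds a second threshold or a minimum change. The mismatch follows from the text alone.

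**2. Width of the printed ranges.** Inputs: the 54 site-by-age cells (6 age bands × 9 sites) for each of pulse, systolic and diastolic pressure in SAP 4.3. Temperature ranges are also printed, but temperature goes to a listing only. Width w = upper limit − lower limit.

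| Sign | Minimum | Median | Maximum | Cells ≤ 10 wide | Cells 5 wide |
|---|---|---|---|---|---|
| Systolic (mmHg) | 5 | 18 | 32 | 7 | 3 |
| Diastolic (mmHg) | 5 | 16 | 26 | 7 | 4 |
| Pulse (bpm) | 15 | 40 | 90 | 0 | 0 |

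Of the 14 blood pressure cells that are 10 mmHg wide or less, 11 belong to site 7, two to site 3 and one to site 1. Two rows show the pattern, with site 7 as the seventh entry: systolic, "1-12 month 80-112 90-112 85-105 90-112 90-112 90-112 75-80 90-112 90-112"; diastolic, "6-9 years 60-78 60-78 55-70 60-78 60-78 60-78 65-70 60-78 60-78".

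**3. Share of readings flagged.** The plan states no such share, so there is no figure to reproduce, and it gives no SD. Assumptions: normally distributed readings recorded as whole numbers; each population centred on its own site's range, which for a given SD gives the smallest share outside; between-child SD of 6–10 mmHg for blood pressure and 10–15 bpm for pulse; all cells weighted equally, because enrolment by site and age is not given.

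Share outside = 2 × (1 − Φ((w + 1) / (2 × SD)))

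Example: w = 12 (systolic 100–112) and SD 8 give (12 + 1)/16 = 0.8125 and a share of 0.417. The same cell gives 0.279 at SD 6 and 0.516 at SD 10. A 5 mmHg range at SD 6 gives 6/12 = 0.5 and a share of 0.617.

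Mean share over cells:

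| Sign | SD | All 54 cells | Without sites 1, 3 and 7 (36 cells) |
|---|---|---|---|
| Systolic | 6 / 8 / 10 | 15% / 26% / 36% | 12% / 23% / 33% |
| Diastolic | 6 / 8 / 10 | 20% / 32% / 42% | 15% / 27% / 37% |
| Pulse | 10 / 15 | 8% / 20% | 3% / 14% |

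The second column drops the three sites whose ranges differ most from the rest. The shares fall but stay material for blood pressure, so agreeing one set of ranges across sites would not remove the problem.

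**4. The same question reversed.** For a centred range to hold 95% of readings, SD = (w + 1)/(2 × 1.96). The median diastolic width of 16 mmHg needs an SD of about 4.3 mmHg, a 5 mmHg range about 1.5 mmHg, and the median pulse width of 40 bpm about 10.5 bpm. A reader with SDs from a suitable source can judge the blood pressure shares from these.

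**The case against.** The strongest reply is that the plan is open about its rule and that other outputs cover the gap. SAP 4.3 prints the rule beside the promise, requires the footnote on site ranges, and summarises changes from baseline. Default summaries include minimum and maximum (protocol 10.1), and every vital sign is listed (listing 12.2.8.9). This stands. A reader might infer that true marked changes would be lost, or that the reported figures would be numerically wrong. The documents support neither: extreme values would appear elsewhere, and the count of readings outside the normal range would be correct. The footnote, however, says whose ranges were used. It does not say that markedly abnormal means no more than outside normal.

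A second reply is that the sponsor's standard Module 2, cited in SAP section 8 but not supplied, may define marked abnormality. It may, but SAP 4.3 states its own rule, and SAP 6.2 adds no specification for the standard tables. If Module 2 has separate limits, SAP 4.3 conflicts with it and still needs correcting.

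Module 2 does matter for two tempting extensions. Because the title of table 10.1.3.2.2 refers to incidence, a reader might infer that readings already out of range at Visit 1 are counted as new. VST002 is a standard output and is not among the non-standard shells in SAP 9.3.1. Its layout is therefore not visible, and the documents do not show that it fails to separate baseline readings. Likewise, the rule in SAP 4.3 is written for the table; that listing 12.2.8.8 applies it is likely from the shared title but not stated.

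A third reply is that the percentages rest on an assumed SD and on equal weights. That is correct. For pulse the share is small in many cells: the median cell is 4% at SD 10. Dropping site 7 alone lowers the systolic and diastolic shares at SD 6 to 11% and 17%.

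**Conclusion.** The point holds as a mismatch between label and rule. Table 10.1.3.2.2 would present any reading outside the site normal range as markedly abnormal; listing 12.2.8.8 would too if it follows the same rule. This part rests on the SAP text and needs no assumption.

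The size is conditional on the assumptions set out in the working. Under them, blood pressure flags run from roughly one reading in seven to two in five, and pulse flags from about one in thirteen to one in five. These shares show scale and do not predict the trial's table: actual enrolment by site and age, and the real SDs, could move them either way.

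The consequence is limited. The table is descriptive, no test is planned on it, and it touches no efficacy endpoint, sample size or decision rule.

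**What to change.** Choose one of two changes in SAP 4.3 and in the output lists (SAP 9.2.1 and 9.2.2):

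- Retitle table 10.1.3.2.2 and listing 12.2.8.8 as 'outside site normal range', and describe them that way in SAP 4.3. This costs only wording. It would leave the marked-abnormality table promised in protocol 10.4 undelivered, so SAP section 7 should record the change.
- If a marked-abnormality table is wanted, as protocol 10.4 says, have the sponsor's medical expert prespecify separate marked limits and use them in place of the normal ranges. This costs the expert's time and the reprogramming of one table and one listing.

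Either way, state in SAP 4.3 whether listing 12.2.8.8 uses the same criterion as the table. A Visit 1 to Visit 2 shift table is an optional addition at the cost of one more table. Neither change nor the optional table needs new data.
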